6.6.1. DAILY DIARY VISIT ASSIGNMENT

The daily diary data do not associate assessments with visits. The date of assessment is collected and will be used to assign the ePRO data to specific visits as required for the definition of various endpoints. The CS7DA4S score is the average of the total daily scores for the 4 CS cardinal symptoms over the 7 days leading up to and including a visit (refer to Section 15.1.1).

The selection of the total daily scores to use to derive CS7DA4S and the 7-day average CS score for the 4 symptoms

for a respective visit is displayed in [Table 2: Daily Diary Visit Assignment](#). For example, in order to derive the Week 2 CS7DA4S, the average of the 7 total daily scores for relative days 9 to 15 will be used.

Table 2: Daily Diary Visit Assignment

Assigned Visit	Target Day	CS7DA4S Range	
		Lower Limit	Upper Limit
Baseline ^a	1	-6	1
Week 1 ^b	8	2	8
Week 2 ^b	15	9	15
Week 3 ^b	22	16	22
Week 4 ^b	29	23	29
Week 8 ^b	57	51	57
Week 12 ^b	85	78	85
Week 16 ^b	113	107	113
Week 20 ^b	141	135	141
Week 24	169	163	169
4 weeks post-treatment ^c	28	21	28
8 weeks post-treatment ^c	56	49	56
12 weeks post-treatment ^c	84	77	84
16 weeks post-treatment ^b	112	105	112
20 weeks post-treatment ^c	140	133	140
24 weeks post-treatment ^c	168	161	168

^a See Section 6.3, the planned timepoint for Baseline is Day 1.

^b For Weeks 2 to 24, target day is calculated relative to the reference start date (refer to Section 6.1)

^c For post-treatment visits, target day is calculated relative to end of treatment date (refer to Section 6.2).

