6.6. WINDOWING CONVENTIONS

All assessments (scheduled, unscheduled, and early termination visits), excluding daily diary data (refer to Section 6.6.1), will be windowed as per [Table 1: Scheduled Visit Windows](#) to ensure all assessments fall into a scheduled visit in order to ensure all data are presented.

If more than one assessment is mapped to the same analysis visit, the following rules for selection of the assessment to use in the analysis will be applied:

- If a nominal and an unscheduled/early termination assessment are mapped to the same analysis visit, the nominal assessment will be selected over the unscheduled/early termination assessment. However, if the nominal assessment result is missing and the unscheduled or early termination assessment result is non-missing, the unscheduled/early termination assessment will be selected.
- In all other scenarios the visit closest to the target day will be selected. If two assessments were performed equally close to an analysis visit’s target day, one prior to and one after, the assessment before the analysis visit’s target day will be assigned to that analysis visit (except for the follow-up MRI assessment which is scheduled to be performed within 7 days after the Week 24/EOT visit).

Table 1: Scheduled Visit Windows

Assigned Visit	Target Day	Visit Windowing	
		Lower Limit	Upper Limit
Screening		-28	-1
Baseline ^a	1	-28	1
Week 2 ^b	15	2	22
Week 4 ^b	29	23	43
Week 8 ^b	57	44	71
Week 12 ^b	85	72	99
Week 16 ^b	113	100	127
Week 20 ^b	141	128	155
Week 24 ^b	169	156	183
4 weeks post-treatment ^c	28	14	42
8 weeks post-treatment ^c	56	43	70
12 weeks post-treatment ^c	84	71	98
16 weeks post-treatment ^c	112	99	126
20 weeks post-treatment ^c	140	127	154
24 weeks post-treatment ^c	168	155	182

^a See Section 6.3, the planned timepoint for Baseline is Day 1.

^b For Weeks 2 to 24, target day is calculated relative to the reference start date (refer to Section 6.1).

^c For post-treatment visits, target day is calculated relative to end of treatment date (refer to Section 6.2).

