15. EFFICACY OUTCOMES

15.1. PRIMARY EFFICACY

15.1.1. PRIMARY EFFICACY ENDPOINT AND DERIVATION

The primary efficacy endpoint is CFBL in CS7DA4S score at Week 4. The 4 CS cardinal symptoms are:

- nasal blockage/obstruction/congestion
- facial pain/pressure
- reduction/loss of sense of smell
- anterior/posterior nasal discharge.

Each symptom is scored on a 4-point scale and is collected on ePRO:

- 0 = none
- 1 = mild
- 2 = moderate
- 3 = severe

The CS7DA4S score is calculated as:

- Add together the four individual symptom scores per day as recorded by the subject to derive the total daily score
 - Total daily scores will only be calculated in cases where all four individual symptom scores are available
- Calculate the average of the total daily scores across the 7 days leading up to and including this visit.
This is the CS7DA4S score at the relevant visit
 - Subject is considered to have sufficient data available to calculate the CS7DA4S score at any given

timepoint if the total daily score is available for at least 5 of the total 7 days

- CS7DA4S scores will be rounded to 1 decimal place

The change from baseline in CS7DA4S at Week 4 will be calculated as detailed in Section 6.7.

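### SAP Table 2 gives 8-day diary windows for a 7-day score at Week 12 and all six post-treatment visits; a minor, separate mismatch affects the baseline week used for the PPAS eligibility check

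*SAP*

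**What the plan says.** **Score definition.** SAP 6.6.1 averages the daily totals "over the 7 days leading up to and including a visit". For Week 2 it says that "the average of the 7 total daily scores for relative days 9 to 15 will be used", which shows that both limits are inclusive. SAP 15.1.1 repeats the rule ("Calculate the average of the total daily scores across the 7 days leading up to and including this visit") and treats a score as available at a "timepoint if the total daily score is available for at least 5 of the total 7 days". SAP 15.2.2.2 applies the same 5-of-7 rule to each individual symptom.

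**Windows.** Table 2 in SAP 6.6.1 has 16 rows giving target day, lower limit and upper limit. Examples are "Week 12 ^b 85 78 85" and "4 weeks post-treatment ^c 28 21 28". The 16-week row reads "16 weeks post-treatment ^b 112 105 112", with footnote b (anchored to treatment start). The same visit in Table 1 reads "16 weeks post-treatment ^c 112 99 126", with footnote c (anchored to end of treatment).

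**Baseline and eligibility.** SAP 6.3 takes baseline from Day -6 to Day 1. SAP 5.6 lists failure of the protocol's entry criteria as a reason for exclusion from the PPAS, and tests CS7DA4S ≥ 7 on seven days that include Day 1. Protocol 8.3.1.1 decides eligibility on the seven days before Day 1 and expressly leaves Day 1 out. Protocol 10.6.1 averages the seven days before the Day 1 and Week 4 visits. SAP 3.3, the list of changes from the protocol, mentions neither difference.

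**The concern.** The text of the SAP and its table cannot both be followed in seven rows. A programmer who uses the table produces an 8-day mean under a 7-day label, with a completeness rule written for a different denominator.

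The scores concerned are:
- **Week 12:** the composite (non-key secondary, SAP 15.2.4.1) and the four symptom scores. Week 12 is also a treatment-stage visit in the GEE (SAP 15.3.3). If later scores are missing, the LOCF sensitivity analysis at Week 24 could carry a Week 12 value forward.
- **Post-treatment:** every diary-based durability score (SAP 15.3.1.4). The LS-means plot to Week 48 would mix 7-day and 8-day averages without saying so.

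The PPAS point is smaller. A check presented as protocol ineligibility uses a different week from the protocol's. It can therefore exclude a correctly enrolled subject or keep one who did not qualify.

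**Working it through.** **1. Window lengths.** Inputs are the Table 2 limits and the day numbering in SAP 6.1 and 6.2. Days = upper - lower + 1, less 1 if the range crosses zero on the study-day scale, because SAP 6.1 has no Day 0. Post-treatment day is a plain date difference from the Week 24/EOT visit (SAP 6.2), so no correction applies there.

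The SAP's own example comes out as stated: Week 2, 15 - 9 + 1 = 7.

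| Row | Limits | Days | Lower limit for 7 days (upper - 6) |
|---|---|---|---|
| Baseline | -6 to 1 | 1 + 6 + 1 - 1 = 7 | unchanged |
| Weeks 1, 2, 3, 4 | 2-8, 9-15, 16-22, 23-29 | 7 each | unchanged |
| Weeks 8, 16, 20, 24 | 51-57, 107-113, 135-141, 163-169 | 7 each | unchanged |
| Week 12 | 78-85 | 8 | 79 |
| 4 weeks post-treatment | 21-28 | 8 | 22 |
| 8 weeks post-treatment | 49-56 | 8 | 50 |
| 12 weeks post-treatment | 77-84 | 8 | 78 |
| 16 weeks post-treatment | 105-112 | 8 | 106 |
| 20 weeks post-treatment | 133-140 | 8 | 134 |
| 24 weeks post-treatment | 161-168 | 8 | 162 |

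So 7 of 16 rows hold 8 days. In all seven the lower limit is upper - 7; in the eight correct post-baseline rows it is upper - 6.

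**2. Effect on a score.** With complete diaries, mean8 - mean7 = (x - mean7)/8, where x is the total on the extra day. If x lies 1 point from the 7-day mean, the shift is 1/8 = 0.125. If it lies 2 points away, the shift is 2/8 = 0.25. These deviations are illustrative. The planning SD for the Week 4 change is 2.4.

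**3. Effect on completeness.** Five days of 7 is 71.4%; five of 8 is 62.5%. Assume each day is completed independently with probability p (not in the documents). The chance of an evaluable score is then P(X ≥ 5):

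| p | 7-day window | 8-day window |
|---|---|---|
| 0.7 | 0.647 | 0.806 |
| 0.8 | 0.852 | 0.944 |
| 0.9 | 0.974 | 0.995 |

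**4. Footnote.** Under footnote b, Days 105-112 would fall within the treatment stage and overlap the Week 16 window (107-113).

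**5. PPAS check.** The protocol week is Days -7 to -1. The SAP week is Day -6 to Day 1. They share 6 of 7 days: Day -7 drops out and Day 1 comes in. With complete diaries:
- A protocol-week sum of 49 gives 49/7 = 7.0, eligible. If the Day 1 total is 1 point below the Day -7 total, the SAP gives 48/7 = 6.857, rounded to 6.9, and the subject fails.
- If Day 1 is 2 points lower, sums of 49 and 50 (7.0, 7.1) fail. If it is 3 points lower, sums of 49 to 51 (7.0 to 7.3) fail.
- In reverse, a sum of 48 (6.9) passes at 49/7 = 7.0 if Day 1 is 1 point higher.

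At the planned 21 evaluable subjects per arm, one misclassified subject is 1/21 = 4.8% of an arm.

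**The case against.** **Table 2.** The strongest reply is that this is a clerical slip whose intended reading is plain. The score is named a 7-day average, three SAP sections say 7 days, nine rows comply, and the daily onset-of-action windows in SAP 15.2.2.1 are spelled out as seven days (2-8, 3-9, 24-30). Programming checks might well catch it. All p-values are nominal (SAP 7.8), and six of the seven rows are exploratory. This limits the weight of the point. It does not remove it, because Table 2 is the operative derivation rule and two programmers could resolve the conflict differently. The footnote letter alone would be trivial, since the row label and Table 1 settle the anchor.

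**PPAS.** The SAP is internally consistent: 5.6, 6.3 and Table 2 all use Day -6 to Day 1, so the check matches the baseline that is analysed. Protocol 8.3.1 has the ePRO completed before any intranasal procedure at clinic visits, so Day 1 is a legitimate pre-treatment value. Protocol 10.1 leaves the PP definition to blinded review. All of this stands. What remains is that the check is labelled as protocol ineligibility while using another week.

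**Stronger readings that the documents do not support.**
- A reader might infer that the primary result is affected by an 8-day window. The Week 4 window (23-29) and the Week 24 window (163-169) each hold 7 days.
- The Baseline row may look like 8 days. With no Day 0 it is 7.
- A reader might infer bias between arms. The same windows apply to every arm, and nothing in the documents points to a differential effect.
- A reader might infer that the SAP always includes the visit day. Treatment-stage windows are fixed to target study days, while the protocol allows the Week 4 to Week 24 visits to fall up to 3 days away. Only at Day 1 is the visit day guaranteed to lie inside the window.

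**Conclusion.** Table 2 contradicts the SAP's own 7-day definition in 7 of 16 rows and should be corrected. The count rests only on the printed limits and the SAP's day numbering. The consequence is confined to the Week 12 non-key secondary scores, the analyses that use them, and the exploratory post-treatment scores. The size is probably small, but the diary data needed to measure it are not in the documents; the score shifts and completeness probabilities above are illustrations under stated assumptions.

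The PPAS mismatch is real but minor. It concerns a supportive analysis set and only subjects close to 7.0, and how many there are is not given. Including Day 1 in the analysed baseline is defensible and need not be reversed. It does need to be declared, as does anchoring the treatment-stage windows to target days where protocol 10.6.1 uses the actual visit.

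**What to change.** 1. In SAP Table 2, set the lower limits to 79 (Week 12) and to 22, 50, 78, 106, 134 and 162 (4, 8, 12, 16, 20 and 24 weeks post-treatment). Give the 16-week post-treatment row footnote c.
2. In SAP 5.6, choose one of two remedies. Either run the CS7DA4S ≥ 7 check on the protocol week (Days -7 to -1), accepting that the analysed baseline of a few PPAS subjects may then be slightly below 7. Or keep Day -6 to Day 1 and call the check an analysis-baseline criterion, not protocol ineligibility.
3. In SAP 3.3, state that the SAP baseline includes Day 1, and that treatment-stage diary windows end on and include the target study day, where protocol 10.6.1 uses the seven days before the actual visit.

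The cost is seven limits, one footnote letter, one PPAS derivation or label, and one entry in 3.3. No new data and no extra analysis are needed.

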#### **4.1.2 Treatment Stage**

The total duration of the Treatment Stage will be 24 weeks. Subjects who complete the study Screening assessments and the washout period and meet all eligibility criteria on Day 1 will be stratified according to the presence or absence of nasal allergy and nasal polyps and, then, randomized in a 1:1:1 ratio to receive LYR-210 (2500 µg), LYR-210 (7500 µg), or sham procedure. Subjects who are assigned to the experimental arms will have the LYR-210 administered bilaterally into the middle meatus (Section 6.2) and, then, removed at Week 24 (Section 6.5). Subjects who are assigned to the sham procedure arm, will undergo bilateral mock administration (i.e., sham procedure) on Day 1. Enrolled subjects will undergo scheduled study visits at Weeks 2, 4, 12, and 24 during the treatment duration. Subjects will receive phone follow-ups at Weeks 8, 16, and 20 to record AEs and concomitant medications/procedures that they have had since last follow-up assessment. [NOTE: Female subjects of childbearing potential will be asked to return to the clinic for urine pregnancy test at Weeks 8, 16, and 20.] All subjects will remain blinded and undergo the assessments and procedures scheduled for these visits (Section 8.1).

At the Week 24 visit, all subjects will return to clinic for the **end-of-treatment (EOT)** visit assessments. Subjects who receive LYR-210 will have bilateral depot removed using standard surgical tools. Sham control subjects will undergo a sham removal procedure to remain blinded.

If medically warranted per the treating physician's discretion (for example, needing an ESS as rescue treatment), early depot removal before the schedule EOT visit at Week 24 may be performed at an unscheduled **early-termination (ET)** visit (an unscheduled EOT visit). Any subject who undergoes an ET visit is required to complete the assessments scheduled for the Week 24/EOT visit, and all safety follow up visits post treatment.

If spontaneous dislodgement of LYR-210 occurs before Week 24 in subjects who receive either dose of LYR-210, subjects are required to call the study clinic immediately to report the event. If

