5.7. PHARMACOKINETIC ANALYSIS SET [PK]

The PK analysis set (PKAS) will contain all subjects in the SAF set who received LYR-210 and have at least one evaluable plasma drug concentration data point post-Day 1 available. As concentration data are required to assign the PK analysis set, this can only be done at study unblinding, at the time of the primary analysis. Subjects will be analyzed according to the actual treatment successfully received.

Subjects who have used any Mometasone Furoate drugs within one day prior to a PK blood draw would be

identified by “MOMETASONE” in the Base Name of concomitant medications. These PK blood draw timepoints will be excluded from analysis. Similarly, results from PK blood draw timepoints after subjects reported any depot dislodgement will also not be analyzed.

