6.2. POST-TREATMENT DAY

The Post-Treatment Day will be calculated for data collected after the Week 24/EOT visit as follows:

$$\text{Post Treatment Day} = \text{date of event} - \text{date of Week 24/EOT visit}$$

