6.4. UNSCHEDULED VISITS, RETESTS AND EARLY TERMINATION DATA

In general, for by-visit summaries, data recorded at the nominal visit will be presented. Unscheduled measurements will not be included in by-visit summaries if a nominal visit is performed in the same visit window but will contribute to the Last Observation Carried Forward (LOCF) value, and the worst-case value where required (e.g. overall post-baseline abnormal summaries).

In the case of a retest (same visit number assigned), the latest available measurement for that visit will be used for by-visit summaries.

Listings will include scheduled, unscheduled, retest and early termination data.

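### SAP Table 2 ties the 16-week post-treatment diary row to the wrong time origin, and SAP Table 1 has no rule for a laboratory or cortisol value that fits two visit rows after early removal

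*SAP*

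**What the plan says.** **Two time origins.** SAP Tables 1 and 2 assign data to visits by date. Footnote b reads "For Weeks 2 to 24, target day is calculated relative to the reference start date" and footnote c reads "For post-treatment visits, target day is calculated relative to end of treatment date". SAP 6.2 adds: "The Post-Treatment Day will be calculated for data collected after the Week 24/EOT visit as follows", namely event date minus the date of that visit.

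**Diary (SAP 6.6.1, Table 2).** Diary entries carry no visit label, so the table alone decides which days make up a score. The 16-week post-treatment row (target day 112, range 105 to 112) carries footnote b. The other five post-treatment rows carry c. In SAP Table 1 the 16-week row also carries c.

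**Everything else (SAP 6.6, Table 1).** The table applies to "All assessments (scheduled, unscheduled, and early termination visits), excluding daily diary data". Its selection rules cover several assessments that map to one visit. They do not cover one assessment that fits two visits. SAP 6.4 says "In general, for by-visit summaries, data recorded at the nominal visit will be presented".

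**After early removal.** Under Protocol 4.1.2 the subject "is required to complete the assessments scheduled for the Week 24/EOT visit, and all safety follow up visits post treatment". Hematology, chemistry and cortisol are drawn at Weeks 4, 12, 24/EOT and 28 (Protocol 8.4.3), and SAP 16.2 summarises them by visit.

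**PK.** SAP 5.7 says that "results from PK blood draw timepoints after subjects reported any depot dislodgement will also not be analyzed". It does not mention draws after removal by the physician. SAP 17 summarises concentrations per dose at each nominal sampling time.

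**The concern.** The protocol separates on-treatment from post-treatment safety. Cortisol and laboratory values at Weeks 4, 12 and 24 belong to a secondary objective. The Week 28 values belong to a separate exploratory objective on safety after treatment. If a value taken four weeks after the depot came out can be counted under Week 12 or Week 24, the by-dose summary for that week mixes exposed and unexposed subjects. For a corticosteroid depot, cortisol is where that mixing matters most.

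The diary footnote raises a similar problem for durability. A programmer who follows Table 2 as printed would report an on-treatment score as the Week 40 durability score, and the diary has no visit label that would expose the error.

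**Working it through.** **The plan's own example.** SAP 6.6.1 says the Week 2 score uses relative days 9 to 15: 15 − 9 + 1 = 7 days. This agrees with the table.

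**Part 1: the 16-week post-treatment diary row.** This row supplies Week 24 + 16 = Week 40.

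| Reading | Origin | Study Days used |
|---|---|---|
| As printed (b) | procedure day | 105 to 112 |
| With c, EOT on Day 169 | end of treatment | 169 + 105 = 274 to 169 + 112 = 281 |

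The Week 16 row is Days 107 to 113. As printed, the two rows share Days 107 to 112, which is 6 of the 8 days. With c they share none.

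**Part 2: double matches in SAP Table 1.** Inputs from SAP Table 1: Week 8 = 44–71, Week 12 = 72–99, Week 20 = 128–155, Week 24 = 156–183, and 4 weeks post-treatment = post-treatment days 14–42 with target 28. For removal on Study Day R, post-treatment day p is Study Day R + p. I assume the 4-week visit is timed from the removal date, as footnote c and SAP 4.2 imply, and takes place on its target day, p = 28.

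- The visit falls in Week 12 when 72 ≤ R + 28 ≤ 99, so R = 44 to 71.
- It falls in Week 24 when 156 ≤ R + 28 ≤ 183, so R = 128 to 155.
- With R = 57 it falls on 57 + 28 = Day 85, exactly the Week 12 target.

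Each of these visits also fits the 4-week post-treatment row, and no sentence says which row prevails.

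**Is there a competing value?** The EOT visit takes place on Day R. R = 44 to 71 is the Week 8 row and R = 128 to 155 is the Week 20 row. The subject's EOT values therefore map to an earlier row than the one the 4-week visit falls in. The off-drug value may be that subject's only entry for Week 12 or Week 24, in which case the selection rules have nothing to choose between.

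**Could the Week 2 to 24 rows simply be closed at removal?** No. The Week 24/EOT ophthalmology examination and the follow-up MRI are due within 7 days after removal (notes to Protocol Table 1; Protocol 8.3.2). The first post-treatment row opens at post-treatment day 14. With a blanket cutoff, an examination on post-treatment days 1 to 7 would fit no row, and the Week 24 IOP and cataract endpoints would lose their data.

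**The case against.** **The footnote is a slip that corrects itself.** Footnote b speaks only of Weeks 2 to 24, the row is labelled post-treatment, and its target is 112 rather than the 113 used for Week 16. SAP Table 1 has c, and superscripts in Table 2 are loose elsewhere (Week 1 carries b and Week 24 carries none). This is persuasive about intent, and only one exploratory time point is involved. It does not remove the need to correct the only specification for those data.

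**The two origins are separated.** A reader might infer that the tables confuse the origins altogether. They do not: the footnotes name the origin for each row, and SAP 6.2 gives later data a Post-Treatment Day. SAP 6.4 prefers the nominal visit, and SAP 6.5 shows Week 24 and EOT data together at a derived EOT time point. All of this stands and makes misassignment less likely. But SAP 6.4 speaks only in general terms, SAP 6.6 windows scheduled visits as well, and Appendix 1 has listings use the visit derived in SAP 6.6. No text closes the Week 2 to 24 rows to later data.

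**PK.** A reader might also infer that post-removal plasma values will be averaged into on-treatment weeks through Table 1. The documents do not show that, because SAP 17 summarises by nominal time. Nor can SAP 5.7 simply drop every post-removal draw, since Week 28 plasma concentration is a planned endpoint. What remains is that SAP 5.7 covers dislodgement and is silent on early removal.

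**Subjects who complete treatment.** With EOT on Day 166, Days 180 to 183 lie in both the Week 24 and the 4-week post-treatment rows (166 + 14 = 180). This has no practical force for the scheduled visit. The Week 28 window is ±7 days, so that visit falls on Days 187 to 201 counted from that EOT (194 ± 7), or on Days 190 to 204 counted from Day 1 (197 ± 7). An unscheduled value on Days 180 to 183 would yield to a non-missing nominal Week 24 value.

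**Conclusion.** Both defects hold, in limited form. Table 2 has the wrong footnote letter on one row; followed literally, it puts on-treatment diary days into the Week 40 durability score. Table 1 lacks a precedence rule, so off-drug laboratory and cortisol values can enter Week 12 after removal on Days 44 to 71, or Week 24 after removal on Days 128 to 155. The documents make this possible, not certain.

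The size cannot be computed, because no early-removal rate and no expected cortisol shift are given. As a scale only, one subject in an arm of 21 (the planned evaluable number for the primary endpoint, not the safety set) carries 1/21 = 4.8% of that arm's mean. The safety summaries are descriptive and have no treatment tests, and neither defect changes the Week 4 primary analysis. The conclusion assumes that the 4-week visit is timed from removal. It is worth correcting because the change is specific and nearly free.

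**What to change.** 1. **SAP Table 2:** change the footnote on the 16-week post-treatment row from b to c.
2. **SAP 6.6:** state that laboratory, cortisol and vital-sign assessments dated after the EOT/removal date map only to post-treatment rows. Assessments scheduled within 7 days after removal (ophthalmology and the follow-up MRI) stay with Week 24/EOT. The first post-treatment row opens at day 14, so also say how an unscheduled laboratory value on post-treatment days 1 to 13 is handled, for example listed only.
3. **SAP 5.7 and 17:** state that PK draws after early removal are not summarised under on-treatment nominal weeks, and that the planned Week 28 post-treatment draw is kept.

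The cost is one footnote letter and a few SAP sentences. No data collection, visit or test changes.
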